1.2 Objectives

The study objectives are 1) to test the impact of the NOHARM intervention on pain and function 3 months following surgery, 2) test the impact of the NOHARM intervention on anxiety and opioid use during the 3 months following surgery.

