4.2 Secondary Objectives

To test the impact of a bundled NOHARM Healing after Surgery Guide + clinical decision support intervention embedded within an EHR on anxiety and opioid use during the 3 months following surgery.

5 **BACKGROUND AND RATIONALE**

5.1 **Background on Condition, Disease, or Other Primary Study Focus**

[figure not shown]
Prescriptions for narcotic pain relief after surgery result in unintended prolonged opioid use for hundreds of thousands of Americans.^{1,2} That trend fuels an excess supply of opioids that can lead to dependence, addiction, diversion, and overdoses on a national scale.³⁻¹⁰ Non-pharmacological pain care (NPPC) is effective and recommended by guidelines for perioperative pain while offering a more favorable risk-to-benefit ratio.¹¹⁻¹⁴ Additionally, patient and clinician decision support interventions are effective in encouraging patient-centered and guideline-concordant care in many other areas of medicine and hold great promise for promoting and facilitating post-operative non-pharmacologic pain management.^{15,16}

5.2 **Study Rationale**

Nonpharmacological pain care is rarely used as first or second-line therapy after surgery, despite guidelines to the contrary.^{17,18} NPPC offers a more favorable risk-to-benefit ratio than opioid medications which may play a critical role in acute post-operative management but should be tapered in favor of safer and more sustainable analgesic options as patients transition home and gradually resume their life roles. Additionally, patient and clinician support interventions have not been tested pragmatically as a bundle in everyday postoperative care as a means of facilitating the uptake of non-pharmacological pain management strategies in the perioperative setting and in the post-acute recovery timeframe. This study will address this knowledge gap and test the impact of utilizing patient and clinician decision support tools to inform patients and facilitate their preference for non-pharmacological pain management modalities.

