6 STUDY DESIGN

This study will utilize a cluster randomized stepped wedge design. Clusters are defined at the level of care teams and qualifying surgical procedures, and have been randomized to one of five different tranches to implement the intervention at staggered intervals (one new cluster each wave, see diagram below).

The primary outcome of the study is a composite of patient reported pain and function at three months post-surgery. This will enable us to determine the effectiveness of a bundled NOHARM Healing after Surgery Guide + clinical decision support for promoting non-pharmacological pain management strategies to patients undergoing qualifying surgeries, which may also ultimately curb overall patient demand for opioid prescriptions in post-acute post-surgical rehab while optimizing functional recovery. Thus, our secondary outcome(s) is opioid use at the 3 month point post-operatively. This will enable us to understand the impact of our EHR-embedded decision support intervention in an era where opioid prescribing is already being constrained.

All patients receiving common, pre-defined procedures within 7 surgical practice areas at 6 Mayo Clinic locations will receive the study intervention if their surgery date coincides with the stepped wedge implementation schedule. Study locations include Mayo Clinic Rochester, Mayo Clinic Florida, and Mayo Clinic Arizona, as well as three Mayo Clinic Health System sites (Mankato, MN; La Crosse, WI; and Eau Claire, WI). Surgical practice areas will include orthopedic surgery, colorectal surgery, gyn surgery, obstetrics, pulmonary/thoracic surgery, liver and kidney transplant, and cardiac surgery. Due to variable combining of post-op unit care areas, practice size, and related considerations we have formed 22 clusters that will be randomized across 5 tranches.

Enrollment in the intervention arm of the trial will extend from March 2021 to approximately August 2023. Participating practices will be enrolled in the study from the point in time the intervention is implemented in their practice and continuing through the end of the study.

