12.4.2 Secondary outcomes

Secondary outcome measures will include opioid consumption, NPPC use, healthcare utilization and anxiety. Anxiety will be measured in a manner similar to physical function and pain interference with a PROMIS CAT administered via the Epic MyChart portal or the Welcome tablet interface prior to a clinic visit that coincides with the 3-month post-surgical time point.

Opioid consumption will be collected using three methods. First, opioid consumption per hospital day, will be extracted from the medication administration log in the EHR. As in previous work,²⁶⁻²⁸ parenteral, transdermal, and oral opioid consumption will be expressed as oral morphine equivalents (OMEs). Second, oral and transdermal opioids prescribed by a Mayo Clinic provider at the time of hospital discharge and during the interval between hospital dismissal and the 3 month post-surgical assessment point will be extracted from the EHR and converted to OMEs. Last, because outpatient prescriptions do not accurately capture opioid consumption, patients will be queried at the 3 month post-operative time point regarding their opioid use using a subscale from a validated opioid consumption questionnaire.²⁸

NPPC use will be collected using two methods. First, the frequency with which patients use specific NPPCs during their hospital stays will be

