3. Opioid use will be measured using 4 outcomes:

- a. Hospital-based consumption, daily oral morphine equivalents (OMEs). This is a continuous measure for each day of hospitalization; we will assume that this depends in part on the day post surgery, D_{ij} and model

$$Y_{ij} = \beta_0 + \beta_I I_{ij} + \beta_D D_{ij} + \beta_T T + \mathbf{B}_X \mathbf{X}_{ij} + \mathbf{B}_Z \mathbf{Z}_j + u_j + e_{ij} \quad (3)$$

For this model we will consider D_{ij} as first continuous and then as categorical.

- b. Discharge and post-discharge prescriptions, daily oral morphine equivalents (OMEs). For this outcome, we will use a model analogous to (3), where D_{ij} is replaced by number of days post discharge.
- c. Number of post-discharge prescriptions. These are counts for the 3 month period following surgery. The impact of the intervention will be assessed using a model similar to (2) but with a Poisson link function:

$$\ln(E(Y_{ij})) \sim \beta_0 + \beta_I I_{ij} + \beta_T T + \mathbf{B}_X \mathbf{X}_{ij} + \mathbf{B}_Z \mathbf{Z}_j + u_j + e_{ij} \quad (4)$$

$$Y_{ij} \sim \text{Poisson}(\mu)$$

We will assess the distribution first using an empty model, and potentially adopt a zero inflated Poisson, negative binomial, or zero inflated negative binomial according to the corresponding AIC values.

- d. Daily use of opioids; this is binary outcome collected one time, at 3 months post-surgery. To assess the impact of the intervention we will use a model similar to (4) but with a logit link:

$$\text{logit}(Y_{ij}) \sim \beta_0 + \beta_1 I_{ij} + \beta_2 T + \mathbf{B}_X \mathbf{X}_{ij} + \mathbf{B}_Z \mathbf{Z}_j + u_j + e_{ij} \quad (5)$$

For a-d we can again test $\beta_1 = 0$ we can assess whether the intervention is associated with changes in the corresponding measure.

4. Healthcare utilization

- a. Hospitalizations
- b. ER visits
- c. Calls to surgical practice

All three of these are count outcomes, and so we will assess the impact of the intervention using a model similar to (4) above. As with (4), we will compare model specifications using an empty model first to determine the best count family (Poisson, negative binomial, zero inflated or not) using AIC, then apply that in the final model.

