13.1.2 Treatment and outcomes variables

The following items will be captured in addition to clinical and demographic variables:

- Patient Reported Medical Information System (PROMIS) computer adaptive test (CAT)
 - Pain interference @ baseline and 1, 2 and 3-months post-surgery
 - Physical functioning @ baseline and 1, 2 and 3-months post-surgery
 - Anxiety @ baseline 3 months post surgery
 - Numerical rating scale pain scores reported q shift during hospitalization
- Pain catastrophizing scale
- TAPS prescription medication use item
- PHQ-4 (four item patient health questionnaire for anxiety (GAD 2) and depression (PHQ 2))
- Opioid prescribing survey
- History of opioids prescribed in one year prior to surgical procedure
- In-hospital administration of medications including oral morphine equivalents and opioid alternatives (i.g., acetaminophen) consumed during

hospitalization

- “Discharge” opioid prescriptions, which may be prescribed prior to the procedure due to clinic workflow
- Opioid prescription orders up to 1 year post-discharge (“refills”)

Data will be programmatically extracted and curated by study team members, including data managers, analysts, and/or statisticians. All data will exist prior to the time of access, and no further patient contact is needed for the above data points.

Once extracted from the EHR, data will be maintained on secure, encrypted, password protected research servers at Mayo Clinic. Access to data files will be restricted to individuals listed in the protocol approved by the Mayo Clinic IRB.

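### Item 3b does not say how opioid prescriptions become daily values; analyse one total OME per patient over the 3 months, zeros kept, with a stated rule for discharge orders written before surgery

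*Combined protocol and SAP*

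**What the plan says.** **Objective.** Section 1.2 sets out to "test the impact of the NOHARM intervention on anxiety and opioid use during the 3 months following surgery", and section 4.2 agrees. Section 6 instead names the secondary outcome as "opioid use at the 3 month point post-operatively".

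**Data.** Section 12.4.2 takes opioid data from three sources. The first is the inpatient administration log. The second is oral and transdermal opioids "prescribed by a Mayo Clinic provider at the time of hospital discharge and during the interval between hospital dismissal and the" 3-month assessment, converted to OMEs. The third is a self-report subscale asked at 3 months, added "because outpatient prescriptions do not accurately capture opioid consumption".

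**Analysis.** Section 12.5 lists four opioid outcomes:
- 3a: inpatient OME for each hospital day, in linear model (3), which has a term for day after surgery and a random intercept for cluster.
- 3b: "Discharge and post-discharge prescriptions, daily oral morphine equivalents (OMEs). For this outcome, we will use a model analogous to (3", with the day term replaced by days since discharge.
- 3c: a count of post-discharge prescriptions over the 3 months after surgery, with Poisson, negative binomial or zero-inflated families allowed.
- 3d: "Daily use of opioids; this is binary outcome collected one time, at 3 months post-surgery".

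**Extraction list.** Section 13.1.2 includes discharge opioid prescriptions, "which may be prescribed prior to the procedure due to clinic workflow". It also lists post-discharge orders up to 1 year and opioids prescribed in the year before surgery.

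**The concern.** An inpatient dose log has a value for every patient-day. A prescription is an order with a date, directions and a quantity. Moving model (3) from one to the other needs three rules that the plan does not give: how an order maps to days, what a patient with no prescription contributes, and when follow-up ends. Section 12.4.2 ends it at 3 months, section 13.1.2 extracts to 1 year, and item 3b gives no end.

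Opioid use is a named secondary objective, and section 6 expects the intervention may lower demand for prescriptions. The result should therefore not depend on an analyst's choice between two layouts, one of which leaves out patients who were prescribed nothing.

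**Working it through.** The documents give no OME mean, SD, sample size or power for any opioid outcome, so there is no planned figure to reproduce. All OME values below are assumed, to show how each reading behaves.

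**Reading A: one row per prescription, value = labelled OME per day.**

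*Quantity.* Total = daily OME × days supplied. At 30 OME/day, supplies of 3, 5, 10 and 20 days total 90, 150, 300 and 600 OME, a 6.7-fold range (600/90). Reading A records 30 for all four. The same directions with half the tablets cut the total by 50% and change Reading A by 0%.

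*Selection.* Per 100 control patients, assume 80 are prescribed, 70 at 40 OME/day and 10 at 20, with equal days supplied. The mean per prescription is (70×40 + 10×20)/80 = 37.5. The mean per patient, zeros kept, is 3,000/100 = 30.0. Now let 10 of the 80 receive no prescription under the intervention:

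| Who is no longer prescribed | Per prescription | Change | Per patient, zeros kept | Change |
|---|---|---|---|---|
| the 10 at 20 OME/day | 2,800/70 = 40.0 | +6.7% | 2,800/100 = 28.0 | -6.7% |
| 10 in proportion to dose group | 37.5 | 0% | 37.5×70/100 = 26.25 | -12.5% |
| 10 of those at 40 OME/day | 2,600/70 = 37.1 | -1.0% | 2,600/100 = 26.0 | -13.3% |

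Prescribing falls in every row. Reading A gives the wrong sign in the first, no effect in the second, and a small part of the fall in the third.

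**Reading B: one row per patient-day, zeros included.** Averaged over an assumed 90 days, the four supplies give 90/90 = 1.0, 150/90 = 1.7, 300/90 = 3.3 and 600/90 = 6.7 OME/day. These are proportional to the totals, so Reading B does track the amount prescribed. Two difficulties remain.
- *Zeros.* With two prescriptions booked on their order dates, 88/90 = 98% of rows are zero. Spread over an assumed 5 days each, 80/90 = 89% are zero. Model (3) is linear with a Gaussian residual. The count and zero-inflated families in section 12.5 are offered for 3c and for healthcare utilization, not for 3b.
- *Repeated rows.* The only random effect is the cluster intercept, so a patient's days are treated as independent given the cluster. For m rows per patient with within-patient correlation ρ, the variance of a patient's mean is understated by a factor of about 1 + (m − 1)ρ. The documents give no ρ, so no figure is put on this.

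**Does 3c fill the gap?** It keeps zeros and covers 3 months, but carries no quantity. By its label it counts only post-discharge prescriptions, so 3b is the only analysed outcome that names the discharge prescription.

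**Orders written before surgery.** Section 12.4.2 opens its window at discharge. Item 3b needs a number of days since discharge, which is negative or undefined for an order that predates the procedure. Section 13.1.2 nevertheless labels such orders as discharge prescriptions. The same list collects opioid history for the year before surgery, so an order of this kind could be filed under either heading.

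**Item 3d.** It is one binary value at one time. A patient who used opioids for 10 weeks and stopped scores the same as one who never used them. That fits the wording of section 6, but not that of sections 1.2 and 4.2.

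**The case against.** The strongest defence is that the text favours Reading B. Model (3) is for a value on each day, and 3b swaps only the day counter. Daily values then add up to the amount prescribed, patients without a prescription contribute zeros, and every row of the table has the correct sign. This stands. A reader might infer that the plan does not measure how much opioid patients were prescribed; the documents do not support that. OMEs are extracted, and under Reading B they are analysed in proportion to the amount. The gap is an unstated derivation together with a poorly suited model.

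The sign reversal needs Reading A, no row for unprescribed patients, and loss of only the lowest-dose patients. It is one scenario among several and not a general result. The zero share likewise depends on how orders are spread over days.

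A reader might also infer that prescriptions written before surgery are dropped. Section 13.1.2 classes them by purpose, and 3b covers discharge prescriptions without a calendar window of its own, so they may be meant to count. What stands is a conflict between three sections.

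Finally, 3d might be read as an error. It matches section 6, persistent use is a stated concern in section 5.1, and 3a does measure inpatient consumption. The self-report subscale may also collect more than the analysed yes/no value. None of this makes 3d a measure of use during the 3 months.

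**Conclusion.** The point holds as a defect of specification and model choice in a secondary outcome; the co-primary outcomes are not affected. As written, two analysts could both follow 3b and report different results. In the assumed examples, a true fall of 6.7% to 13.3% in OME per patient appears under Reading A as anything from +6.7% to -1.0%, and a halved quantity appears as no change. Under Reading B the direction is right, but 89% to 98% of rows are zero with two prescriptions in 90 days, and repeated days within a patient are not modelled.

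These sizes rest on assumed doses, days supplied and prescribing rates. The qualitative result needs only the wording of sections 12.4.2, 12.5 and 13.1.2. No analysed post-discharge outcome is defined as a 3-month total prescribed or taken, although the data for the prescribed total are already extracted. Loss of pre-surgery discharge orders remains a risk, not something the documents establish.

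**What to change.** 1. In section 12.5, replace 3b with one value per patient: total OME prescribed from the discharge prescription to the 3-month point, with zero for patients who had no prescription. Use a model suited to zero-heavy, skewed data, for example a two-part model, or a log link with robust or cluster-adjusted errors. If a two-part model is used, report the effect on the overall mean, because the second part alone again conditions on being prescribed.
2. In section 12.4.2, define the discharge prescription to include orders written before the procedure for post-operative use, in line with section 13.1.2. State how these are told apart from prior opioid history, and that orders after the 3-month point are not counted.
3. Reconcile sections 1.2 and 4.2 (use during the 3 months) with section 6 (use at the 3-month point). Keep 3d and describe it as persistent use at 3 months.

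Adding the opioid item to the 1- and 2-month questionnaires mid-trial is not recommended. Under section 7.3, control data are collected before a cluster is activated, so the new item would be missing mainly for control-period patients.

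The cost is revised wording, one extraction rule and a little analysis work on data already planned for extraction. The day-by-day course after discharge is lost as a model result, but can be kept as a descriptive display.

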12.5 Data Analyses

Because patients are randomized in clusters, all statistical methods will account for potential correlation of measures within clusters. Such methods include cluster adjusted standard errors for t-tests and χ^2 -tests, and mixed effects models. Patient characteristics will be summarized by intervention status, and tested for difference between intervention groups; any factors which are imbalanced will be accounted for in the main analyses. Factors assessed for balance and potential inclusion in pre-specified analyses are those listed in Section 13.1.1 and all baseline measures listed in 13.1.2.

The primary and secondary outcomes will be compared between intervention groups using mixed effects generalized linear models. Each model will include an indicator for intervention group; a random intercept for cluster; cluster level factors that were used to constrain randomization; calendar time; surgery type; and any patient factors that were imbalanced across groups.

The model details for each outcome are as follows:

1. PROMIS CATs (anxiety (1°), physical function (1°), pain (1°)). These are continuous measures, collected at two time points, pre-operative and 3 months post-operative. To assess the impact of the intervention on these we will estimate three separate models. If Y_{ijt} is the measure at time $t=1,2$ of the i th patient treated by the j th cluster, then we will estimate

$$Y_{ij2} = \beta_0 + \beta_I I_{ij} + \beta_B Y_{ijo} + \beta_T T + \mathbf{B}_X \mathbf{X}_{ij} + \mathbf{B}_Z \mathbf{Z}_j + u_j + e_{ij} \quad (1)$$

where I_{ij} indicates the intervention status, T is calendar time, $u_j \sim N(0, \tau^2)$ is a cluster level random effect, X_{ij} is a vector of patient characteristics, including surgery type, Z_j is a vector of cluster characteristics used for randomization, and e_{ij} is a residual error. By testing $\beta_I = 0$ we can assess whether the intervention is associated with changes in the corresponding measure.

2. NPPC use. This is collected as a binary value for each of 14 modalities, collected at one time point, 3 months post-operative. We will sum these to create a score, and use a model similar to (1) but without a baseline value Y_{ij0} :

$$Y_{ij} = \beta_0 + \beta_I I_{ij} + \beta_T T + \mathbf{B}_X \mathbf{X}_{ij} + \mathbf{B}_Z \mathbf{Z}_j + u_j + e_{ij} \quad (2)$$

Again by testing $\beta_I = 0$ we can assess whether the intervention is associated with changes in the corresponding measure.

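### Models (3)–(5) fix no baseline opioid term, and the opioid history that can enter by balance test has a window open to discharge prescriptions written before surgery

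*Combined protocol and SAP*

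**What the plan says.** Section 12.5 fits PROMIS outcomes with model (1), which always carries the pre-operative value. For NPPC use it will "use a model similar to (1) but without a baseline value"; that is model (2).

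Item 3 lists four opioid outcomes:
- 3a, daily in-hospital OME, and 3b, discharge and post-discharge OME, use model (3). Its added term is the day: "we will assume that this depends in part on the day post surgery" (for 3b, days since discharge).
- 3c, the number of post-discharge prescriptions: "The impact of the intervention will be assessed using a model similar to (2) but with a Poisson link function". This is model (4).
- 3d: "Daily use of opioids; this is binary outcome collected one time, at 3 months post-surgery". Model (5) has the right-hand side of (4) with a logit link.

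None of (3)–(5) prints a baseline opioid term. All contain the patient vector X, and 12.5 puts into every model "calendar time; surgery type; and any patient factors that were imbalanced across groups". The candidates are wide: "Factors assessed for balance and potential inclusion in pre-specified analyses are those listed in Section 13.1.1 and all baseline measures listed in 13.1.2".

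Section 13.1.2 lists "History of opioids prescribed in one year prior to surgical procedure". The same list has an item for discharge "opioid prescriptions, which may be prescribed prior to the procedure due to clinic workflow". Section 12.6.2 uses pre-operative opioid use to define risk of prolonged use, without giving it a window.

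**The concern.** Opioid use is a stated secondary objective (4.2). A plausible predictor of it is extracted in both conditions, but whether it is used depends on a balance test.

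That route also has a measurement problem. The history window ends at the procedure. Patients are on study from the decision to have surgery (1.4), and the surgery order triggers the Guide message (8.1). A discharge prescription written between order and operation is therefore post-exposure, yet it falls inside the window. It is also part of outcome 3b. If the intervention lowers such prescriptions, the recorded history differs between conditions, may be selected as imbalanced, and then absorbs part of the effect it should leave alone. Repairing the selection rule alone would leave this window open. Fixing the term without closing the window would build the problem in.

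**Working it through.** **The plan's own figure.** The only precision figure is in 12.2: a detectable effect of 0.048–0.055 SD for pain. No opioid power is given. The Hussey–Hughes formula with 22 clusters, 6 periods, σ² = 1 and 114,000 patients spread evenly gives SE 0.0106. The detectable effect is then 2.80 × 0.0106 = 0.030 SD at 80% power, or 3.24 × 0.0106 = 0.034 SD at 90%. Section 12.2 does not state alpha, power or the analysed number, so its figure can be neither confirmed nor called wrong.

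**Power gain from a fixed, clean term (linear models).** Assumed: two-sided 0.05, 80% power without the term, and r, the correlation of history with outcome net of surgery type and cluster. The SE scales by √(1 − r²), so power = Φ(2.80/√(1 − r²) − 1.96).

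| r | SE ratio | Power |
|---|---|---|
| 0.1 | 0.995 | 80.4% |
| 0.3 | 0.954 | 83.6% |
| 0.5 | 0.866 | 89.9% |

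For the logit model, an illustration without clustering (assumed 20% prior use, 3% base risk, treatment odds ratio 0.85, 12,000 per arm, 400 runs) gave 68% to 70% when history has odds ratio 3, and 80% to 89% when it has odds ratio 20.

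**Attenuation of 3b.** Let Y be the outcome and H the clean history, both in SD units, with correlation r. The intervention lowers Y by d. A share q of discharge prescriptions is pre-written and enters the recorded history with weight w and mean shift m: H* = H + P·w·(Y + m), where P = 1 with probability q.

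- Shift in mean H* between conditions: −q·w·d.
- Within-condition slope of Y on H*: b = (r + qw) / [1 + qw²(1 + m²) − (qwm)² + 2qwr].
- Adjusted effect: −d(1 − q·w·b). The proportion lost is q·w·b.

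| r | m | w | q | b | Lost |
|---|---|---|---|---|---|
| 0.5 | 0 | 1 | 0.10 | 0.6/1.2 = 0.500 | 5.0% |
| 0.5 | 0 | 1 | 0.25 | 0.75/1.5 = 0.500 | 12.5% |
| 0.5 | 0 | 1 | 0.50 | 1.0/2.0 = 0.500 | 25.0% |
| 0.3 | 2 | 1 | 0.10 | 0.4/1.52 = 0.263 | 2.6% |
| 0.3 | 2 | 1 | 0.50 | 0.8/2.8 = 0.286 | 14.3% |
| 0.5 | 2 | 1 | 0.10 | 0.6/1.56 = 0.385 | 3.8% |
| 0.5 | 2 | 1 | 0.50 | 1.0/3.0 = 0.333 | 16.7% |
| 0.5 | 0 | 0.5 | 0.25 | 0.625/1.188 = 0.526 | 6.6% |
| 0.5 | 0 | 0.25 | 0.25 | 0.5625/1.078 = 0.522 | 3.3% |

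Simulation with 400,000 records gave slopes of 0.263, 0.289, 0.387 and 0.337 for the four m = 2 rows, in agreement. With w = 1 the loss is roughly 3–5% at q = 0.10 and 15–25% at q = 0.50. Smaller weights give less. If the intervention leaves pre-written prescriptions unchanged, the shift in H* is zero and nothing is lost.

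**Could the history be selected?** The shift in H*, in its own SDs, is 0.5 × 0.05/√3 = 0.014 for d = 0.05 (r = 0.5, m = 2, w = 1, q = 0.5) and 0.5 × 0.20/√2 = 0.071 for d = 0.20 (same r, w and q, m = 0). Section 12.5 gives no threshold. If p < 0.05 is used, an imbalance of 0.03 SD is flagged with probability Φ(0.03/0.0106 − 1.96) = 81%. With the SEs implied by 12.2 at 80% power (0.048/2.80 = 0.0171 and 0.055/2.80 = 0.0196), it is about 42% and 33%. Selection is plausible, not certain.

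**The case against.** The strongest reply is that opioid history is not shut out. Models (3)–(5) contain X, and 12.5 names the baseline measures of 13.1.2 as candidates. This stands: a reader might infer from the equations that baseline opioid use is excluded, and the documents do not support that. What remains is that entry depends on the data.

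Second, model (1) is an imperfect comparison. In-hospital OME has no pre-operative counterpart and 3d is asked once, so history is a prognostic covariate there and not the same measure taken earlier. This also stands, but fixed entry of a prognostic covariate is still better than entry by balance test.

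Third, double counting is inferred from silence. Discharge prescriptions are a separate item in 13.1.2, and the note on timing may be meant to classify early ones as discharge prescriptions only. That is a fair reading; the text has no rule that settles it.

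Fourth, the intervention may not reach these prescriptions. Section 8.1 places selection-driven clinician prompts after surgery, and the timing of the opioid-prescription alert in Appendix B is not stated. If they are unaffected, there is no attenuation.

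Fifth, power may not be short. If the pain precision in 12.2 carried over to opioids at 80% power, an effect of 0.20 SD would be 0.20/0.0196, or about 10 standard errors, and the power gain would be nil. This limits the power argument but does not touch the window.

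**Conclusion.** The point holds as a gap in specification. No baseline opioid term is fixed in (3)–(5), the history enters only through a balance test, and its window can admit post-exposure prescriptions.

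Three stronger readings go too far:
- That all four outcomes overlap with the history. The overlap is exact for 3b only; for 3a, 3c and 3d a pre-written prescription is a post-exposure covariate, not part of the outcome.
- That the plan states it will count these prescriptions twice. It only lacks a rule against it.
- That a definite amount of power is lost. The gain from the fixed term runs from negligible at r = 0.1 to about 10 points at r = 0.5, and only from an assumed 80%.

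The attenuation figures likewise rest on an assumed share, scaling and correlation, and on the intervention changing pre-written prescriptions. The primary PROMIS comparisons carry their own baseline, and this point is not about them. It is worth correcting because the data are already extracted and the change is small.

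**What to change.** In 12.5 item 3, include pre-operative opioid prescribing as a fixed covariate in (3)–(5) for all four outcomes, regardless of balance. An amount on a log scale, log(1 + OME), plus an any/none indicator would serve.

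In 13.1.2, define it over a one-year window ending before the surgery order or the decision for surgery, and exclude any order classed as a discharge prescription for the index surgery. Count those orders only in 3b. Name the anchor date for each practice, since the documents do not describe order timing in obstetrics or transplant. Use the same definition for pre-operative opioid use in 12.6.2.

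The cost is SAP wording, one date rule in the existing extraction and one or two model terms; no new data are needed. There are two small drawbacks. The odds ratio in (5) becomes conditional on history, as it already is on the other covariates. Opioids prescribed outside the health system stay unmeasured, which reduces the gain.
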